
**(9) Stress experienced in session** will be assessed via ECG. Children will be connected to a UFI 3991/4 EIRS BioLog ambulatory physiological data recorder using disposable Ag/AgCl electrodes prior to the start of treatment sessions 1, 4, 6, 8, and 12. Placement of electrodes will be performed by a research assistant using the procedures specified previously. Event marks will be recorded at the point of transition from the 10-minute

relaxation/pleasurable activities time to the start of the implementation of techniques. RSA will be sampled in 30 second epochs and calculated for each of these two time periods (10 minute phase prior to technique implementation, 45 minute phase of technique implementation). This methodology will allow for assessment of within-participant RSA trajectories over the course of treatment, and between-group comparisons on physiological stress response both prior to and during technique implementation. **(10) Quality of therapeutic rapport** will be assessed via child and caregiver-report using the appropriate versions of the Therapeutic Alliance Scale for Children-Revised (TASC-R; Accurso et al., 2013; Creed & Kendall, 2005; Shirk & Saiz, 1992). AAT is believed to facilitate the development of rapport and, therefore, assessing rapport at multiple points in the first phase of treatment is appropriate. As such, rapport will be assessed at the 2nd and 4th treatment sessions as well as at post-treatment. A research assistant will administer the TASC-R with caregivers and children during these sessions and will explicitly state that the clinician will not be made aware of the answers provided. **(11) Attitudes toward pets** will be assessed for the youth at the pre-treatment assessment only using the Pet Attitude Scale to determine whether pre-existing attitudes toward pets is related to outcome in the TF-CBT+AAT group. **(12) The demographics** form will be completed at the pre-treatment assessment only.

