Modified variance estimators are calculated to reduce bias when sample sizes are small and t-tests are used for valid inference. The analysis will be conducted using the function of “geesmv” in R (Wang et al. 2016). Similar methods can be used for the analysis of canine heart rate variability and behavior.

With regards to the ECG data, interrupted time series analyses can be used to analyze RSA from two time periods. The covariates of interest include time (in minutes) since the start of RSA assessment, the treatment group (0 = TF-CBT; 1 = TF-CBT+AAT), the time period (0 = phase prior to

technique implementation; 1 = technique implementation), time (in minutes) since technique implementation, and the interactions of the last variables with the treatment group. The correlation among time series observations is represented in the error term. Residual plots can be used to detect the autocorrelation, where the Durbin–Watson statistic can be used. This model can be fitted by SAS PROC AUTOREG v. 9.4. Regression-based mediational analyses can be conducted at each of the four assessment sessions to examine if therapeutic rapport mediates the relationship between the presence of the dogs and PTS outcomes. Bootstrap or Monte Carlo methods can be applied to testing significance of the indirect effect (Tofighi & MacKinnon, 2015). This model can be fitted using the PROCESS macro for SAS v. 9.4 (Hayes, 2013).

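### The in-session RSA model names no child, session or dog term, so the standard error of the between-group RSA level is generally too small

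*Combined protocol and SAP*

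**What the plan says.** Section 4.2, Measures, item 9 records the child's ECG in five treatment sessions (1, 4, 6, 8 and 12). There, "RSA will be sampled in 30 second epochs and calculated for each of these two time periods": the 10 minutes before techniques begin and the 45 minutes of techniques. Two aims follow. One concerns change over sessions ("This methodology will allow for assessment of within-participant RSA trajectories over the course of treatment"). The other is "between-group comparisons on physiological stress response both prior to and during technique implementation".

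Section 5.2, Statistical methods, states that "interrupted time series analyses can be used to analyze RSA from two time periods". The covariates are time, group, period, time since techniques began, "and the interactions of the last variables with the treatment group". On dependence it says "The correlation among time series observations is represented in the error term". The checks are that "Residual plots can be used to detect the autocorrelation", together with the Durbin-Watson statistic. On software: "This model can be fitted by SAS PROC AUTOREG v. 9.4".

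The same section allows for clustering elsewhere. The multilevel models for PTS, emotional and behavioral concerns, and emotion regulation nest AAT-arm youth by dog, and the dog cortisol analysis uses GEE with small-sample variance corrections. Nothing equivalent is stated for in-session RSA.

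**The concern.** Group does not vary within a child, so information on the difference in RSA level comes from 60 children and not from thousands of epochs. With no child term, the only allowance for similarity within a child is the serial error, which absorbs part of it. A chance difference in RSA level between two sets of 30 children could then be reported, with too narrow an interval, as an effect of the dog.

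Two gaps in wording add to this.

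- The session-trajectory aim is not clearly assigned to a model, and the plan does not say whether the five sessions are fitted jointly.
- It is unclear which variables are interacted with group. If only period and time since techniques began are meant, group-by-time is omitted and pre-technique slopes are forced equal across arms, although the dog is already in the room in those 10 minutes. The mean model itself may then be wrong.

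**Working it through.** **Inputs from the documents.** 60 children in equal arms give 30 per arm. Epochs: 10 min / 30 s = 20 and 45 min / 30 s = 90, so 110 per child-session, 60 × 110 = 6,600 per session and 33,000 over five sessions. Three dogs give about 10 children per dog if spread evenly (assumed).

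**The plan's own figure.** None is given for RSA. The only power statement concerns the UCLA score: (1.96 + 0.84) × 6.5 × √(2/30) = 4.70 points, consistent with the stated approximately 5. It does not bear on this point.

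**Why serial error is not enough.** Assume a child SD of 0.5 and an epoch SD of 0.8. The ICC is 0.25 / (0.25 + 0.64) = 0.28. With within-child lag-1 correlation 0.3:

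- the correlation at lag 1 is 0.28 + 0.72 × 0.3 = 0.50;
- at lag 10 (five minutes) it is still 0.28;
- an AR(1) error matched at lag 1 implies 0.50^10 = 0.001 at lag 10.

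The persistent part is almost entirely missed.

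**Null simulation (assumed variances).** One session, 30 children per arm, 110 epochs, Yule-Walker fits with AR(1), AR(2) and AR(5), 800 runs per cell. Child SD / epoch SD of 0.5/0.8 and 1.0/0.7 give ICC 0.28 and 0.67. Children either did or did not differ in phase change (SD 0.4) and slope (SD 0.01/min). False-positive rate for group level, nominal 5%:

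| How children enter the fit | Group-by-time | Lag-1 0.3 | Lag-1 0.7 |
|---|---|---|---|
| Stacked, sorted by arm | omitted | 16–34% | 21–31% |
| Stacked, sorted by arm | included | 8–18% | 16–28% |
| Stacked, random order | omitted | 19–44% | 29–54% |
| Stacked, random order | included | 10–43% | 29–55% |
| Error restarted at each child | omitted | 9–29% | 10–18% |
| Error restarted at each child | included | 3–9% | 5–6% |

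At ICC 0.10 (child SD 0.3, epoch SD 0.9), lag-1 0.3 and a sorted file, the rates are 11–16% without group-by-time and 6–8% with it. At ICC 0 and lag-1 0.3, stacked fits give 5–6%, so there the excess is due to child variance. At lag-1 0.7, stacking alone gives 7–17% with no child variance, so part of the excess there comes from running the children together as one series.

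**Standard error and diagnostics (sorted file).** The reported standard error averages 0.49–0.75 of the true one without group-by-time and 0.56–0.90 with it. Durbin-Watson after AR(2) or AR(5) averages 2.00–2.10, so it looks clean while the standard error is wrong.

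**Row order.** With AR(1), lag-1 0.3 and no group-by-time, reordering the children changed the 5% verdict on group level in 30% of datasets at ICC 0.28 and 83% at ICC 0.67.

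**Five sessions pooled.** Over wider assumptions (total variance 1; child variance 0.1–0.7, session variance 0–0.2, dog variance 0 or 0.05 added on top, autocorrelation 0.3–0.95; several layouts), the ratio of reported to true standard error was 0.08–0.53 with five sessions and 0.17–0.71 with one.

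**Interaction tests.** These have no single direction. At lag-1 0.3 they reject in 0–9% of runs, except group-by-time-since at 8–21% (random order, ICC 0.67, AR(2) or AR(5), no group-by-time). At lag-1 0.7 without group-by-time, group-by-period rejects in 2–14%; group-by-time-since rejects in 10–22% (sorted), 10–36% (random order) and 0–3% (restarted).

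**Omitted group-by-time.** Suppose the arms differ in pre-phase slope by 0.01/min and the difference then plateaus at 0.01 × 10 = 0.10. With epochs timed 0, 0.5, …, 9.5 min (mean 4.75), the fitted pre-phase group difference is 0.01 × 4.75 = 0.0475. The fitted jump is 0.10 − 0.0475 = 0.0525 and the fitted slope change is 0. The true values are 0, 0 and −0.01; adding group-by-time recovers them.

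**The case against.** The strongest reply is that the text is permissive: the analyses, covariates and software are offered as options, so a sound version could still be run. That is fair. The gap is in what is specified, and it does not show how the data will be analysed. But no other model is named for in-session RSA, and the choices that make it sound are not stated.

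Second, every magnitude rests on assumed variances, autoregressive order and layout, and on PROC AUTOREG fitting one series without subject or random terms. This stands. No figure above is this trial's error rate, and one combination is about nominal.

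Third, the multilevel models in section 5.2 cover emotion regulation, and item 3 of the Measures calls RSA a marker of it, so the session-trajectory aim might be served there. Item 3, however, concerns RSA before and after treatment; in-session RSA is item 9, with its own model.

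Fourth, effect-size estimation for a larger trial is a stated primary objective, and the RSA paragraph sets no significance level. Interval width therefore matters more than false positives. That tempers the severity, but width is exactly what goes wrong.

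**Conclusion.** The concern holds. Confidence is high that the terms are not named and that the standard error of group level is generally too small when children differ in RSA level. Confidence is moderate on size: one-session simulations of stacked children at ICC 0.28–0.67 give roughly two to eleven times the nominal 5% (8–55%). The conclusion concerns the between-group level and should not be extended to the interaction tests as a general inflation. The level estimate stays centred only if the mean model is right; with group-by-time omitted and unequal pre-phase slopes it does not. The documents do not rank in-session RSA among the outcomes. The PTS analysis has its own model and is unaffected. This should be fixed before analysis.

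**What to change.** Make the child the unit of inference. The simplest route is to compute each child's mean RSA in each phase, which item 9 already plans, the change between phases, and the child's slope over sessions. Compare the arms on these, carrying over the partial nesting by dog. With no dog effect, child-level t-tests on phase means and change reject in 3.2–6.8% of null runs. Dog still matters. With 3 dogs of 10 children against 30 un-nested, at dog ICC 0, 0.05 and 0.10, a t-test ignoring dog rejects in 4.9%, 7.7% and 10.7%; a Welch test on dog means gives 5.5%, 6.0% and 6.4%.

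The alternative is a linear mixed model with child and child-by-session effects, AR(1) errors within child-session, dog nesting and small-sample degrees of freedom. If sessions are fitted jointly, add session, session-by-group and a random child slope over sessions.

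In any model, include group-by-time, name every interaction, state the time origin that gives the group term its meaning, and say which model serves the session-trajectory aim.

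The cost is SAP wording and some programming on the same data. Intervals widen: at those three dog ICCs the dog-aware child-level interval is on average 17%, 39% and 61% wider than one ignoring dog. The mixed model's level test is conservative (0.8–4.0%) with dog-based degrees of freedom and ranges over 2.8–8.5% with 58, so that choice must also be stated in advance.

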# Integrating Animal-Assisted Therapy Into Trauma-Focused Cognitive-Behavioral Therapy for Maltreated Youth (TF-CBT+AAT) Protocol

## 1.0 Inclusion and Exclusion Criteria

### 1.1 Inclusion Criteria

#### Minor Patients

- Age 6-17 years (inclusive) with a participating consenting caregiver with legal standing to consent for the minor child (either biological parent or adoptive parent). All youth will be asked to provide assent.
- Sex: male or female
- Fluent in written and spoken English, as the assessment instruments are not available in translations and have not been validated for use with non-English speaking populations.
- An allegation of abuse or neglect investigated by law enforcement or child protective services.
- A raw score of  $\geq 39$  on the caregiver-report version of the UCLA PTSD Reaction Index completed by the caregiver upon presentation to the TLC Clinic or the Pinnacle Health Children's Resource Center (CRC).
- A full scale IQ score of  $\geq 80$  on the Kaufman Brief Intelligence Test (2nd ed.; KBIT-2)

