## 4.0 Study Design and Procedures

### 4.1 Study Design

Randomized clinical trial with two active conditions and no placebo or waitlist conditions.

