## **Measures**

**(1) Posttraumatic stress (PTS)** will be assessed primarily through caregiver-report on the UCLA PTSD Reaction Index. In addition to the pre-treatment/referral and post-treatment assessments discussed above, the caregiver will complete the UCLA when presenting for the 5th treatment session (score after the first phase of treatment [sessions 1-4]) and the 9th treatment session (score after the second phase of treatment [sessions 5-8]). Thus, PTS will be assessed at four separate points in the treatment process, which will allow for a comparison of the rate of progress across the two conditions. Children will also complete the self-report version of the UCLA at each of the four assessment points. **(2) Emotional and behavioral concerns** will be assessed by caregiver-report using the Strengths and Difficulties

Questionnaire (SDQ; Goodman, 1997). As with the UCLA, the caregiver will complete the SDQ at pretreatment, during sessions 5 and 9, and at post-treatment. Children will self-report their anxiety concerns on the Screen for Child Anxiety Related Disorders (SCARED; Birmaher et al., 1999) and their depression concerns on the Mood and Feelings Questionnaire (MFQ; Angold et al., 1995) at each of the four assessment points. A research assistant will be responsible for administering measures at each assessment.

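### Rapport mediation is planned at all four PTS assessments, but one of them has no rapport score, and the mediator and covariates for the other three are not specified

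*Combined protocol and SAP*

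**What the plan says.** The mediation plan is at the end of section 5.2 (Statistical methods): "Regression-based mediational analyses can be conducted at each of the four assessment sessions to examine if therapeutic rapport mediates" the path from the dogs to PTS. It names bootstrap or Monte Carlo testing of the indirect effect and the software. It does not name the TASC-R occasion, the informant or any covariates.

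The measurement schedule is in section 4.2 (Measures).

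- **PTS, item 1.** It "will be assessed primarily through caregiver-report on the UCLA PTSD Reaction Index", with a child self-report version alongside. There are four occasions: pre-treatment/referral, session 5, session 9 and post-treatment. For the second, "the caregiver will complete the UCLA when presenting for the 5th treatment session (score after the first phase of treatment [sessions 1-4".
- **Rapport, item 10.** It "will be assessed via child and caregiver-report using the appropriate versions of the Therapeutic Alliance Scale for Children-Revised". On timing, "rapport will be assessed at the 2nd and 4th treatment sessions as well as at post-treatment". The reason given is that the dog is expected to help rapport form, so "assessing rapport at multiple points in the first phase of treatment is appropriate".

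Section 1.1 requires a minimum score "on the caregiver-report version of the UCLA PTSD Reaction Index completed by the caregiver upon presentation to the TLC Clinic" or the CRC, so every entrant has a baseline caregiver UCLA.

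Earlier in section 5.2 (Statistical methods), gender, age and number of trauma types are given as examples of possible confounders. They are attached to the multilevel trajectory models.

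**The concern.** The number of mediation models follows the PTS schedule, but the mediator was collected on a different schedule. One planned model has nothing to put in the mediator position. For the rest, an unstated pairing rule decides something important: whether rapport is measured before the PTS outcome or at the same visit. At the same visit, a child who has improved may rate the clinician more warmly, so symptom change could produce the rapport difference and not the reverse.

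The design is described as "Randomized clinical trial with two active conditions and no placebo or waitlist conditions". Randomization protects the comparison of arms, including the arm-to-rapport path. It does not protect the rapport-to-PTS path, because rapport is not assigned. A child with milder symptoms at entry may both form rapport more easily and finish with lower PTS. Without named covariates, that path is open to confounding.

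The mediation sentence is also the only planned use of the TASC-R data in the statistical methods, and section 5.2 (Sample size determination) says that estimates from this trial are meant to inform a larger one. A mechanism result could be carried forward.

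**Working it through.** **Inputs.** PTS occasions: pre-treatment, session 5, session 9, post-treatment (Measures, item 1). TASC-R occasions: session 2, session 4, post-treatment (Measures, item 10). Planned models: four. No other outcome schedule in the document fits that count together with the PTS outcome.

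**Model.** With arm A, rapport M, PTS outcome Y and covariates X:

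- mediator regression: M = i1 + a·A + X terms + error
- outcome regression: Y = i2 + c′·A + b·M + X terms + error
- indirect effect: a·b

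Both regressions need a value of M.

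**Cross-tabulation.**

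| PTS assessment | TASC-R at the same visit | TASC-R taken earlier |
|---|---|---|
| Pre-treatment | none | none |
| Session 5 | none | sessions 2 and 4 |
| Session 9 | none | sessions 2 and 4 |
| Post-treatment | post-treatment | sessions 2 and 4 |

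- Same-visit rapport: 1 model can be run, so 4 − 1 = 3 cannot, and the one left is concurrent.
- Earlier rapport: 3 models can be run, so 4 − 3 = 1 cannot.
- Pre-treatment fails in both columns.

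**Separation with session-4 rapport.** Sessions are weekly (section 4.2). The nominal gap to the session-5 UCLA is 5 − 4 = 1 week, and to session 9 it is 9 − 4 = 5 weeks. Post-treatment falls within 2 weeks of session 12, so that gap is 12 − 4 = 8 to 8 + 2 = 10 weeks. The session-5 model is therefore close to concurrent.

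**What session-4 rapport can already contain.** No UCLA is taken between pre-treatment and session 5. Step 5 of the session structure places the research assistant's data collection with the child after the child's own treatment component. A child TASC-R at session 4 can therefore reflect symptom change up to and including that session.

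**Illustration only.** The plan gives no rapport effect or rapport–PTS correlation, so the following rests on assumed values. The plan's one effect-size figure is the power statement. With 30 per arm, SD 6.5 and two-sided .05, the difference detectable with 80% power is (1.96 + 0.84) × 6.5 × √(2/30) = 4.70 points (about 4.78 by the t distribution), in line with the stated approximate 5. In SD units 5/6.5 = 0.77, which is a detectable difference and not an expected one.

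Simulated trials (4,000 per case, 30 per arm, no true effect of rapport on PTS, within-arm rapport–symptom correlation −0.2 to −0.5) gave these shares with a significant indirect effect:

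| Group difference in PTS | Concurrent post-treatment rapport | Session-4 rapport, one third of the difference present early | Session-4 rapport, all of it present early |
|---|---|---|---|
| 0.3 SD | 1.2% to 9.2% | 0.7% to 5.1% | 1.0% to 8.0% |
| 0.5 SD | 1.6% to 16.3% | 0.9% to 5.3% | 1.1% to 14.4% |
| 0.77 SD | 2.8% to 32.5% | 0.9% to 7.4% | 1.5% to 28.5% |

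The session-4 columns assume a 0.8 correlation between early and later change. Of the 36 cases behind this table, 21 are below 5%.

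For baseline adjustment, with a 0.5 SD arm difference in rapport, the result depends on how baseline UCLA correlates with later PTS and with rapport. At 0.6 and −0.4 the rates are 18.9% for the raw score, 11.1% for a change score and 2.3% with baseline as covariate. At 0.2 and −0.1 they are 2.1%, 2.7% and 2.1%, so adjustment gains nothing there.

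**The case against.** A reader might infer that only a concurrent post-treatment model is left, or that the mediation plan as a whole cannot be carried out. The documents do not support either. Nothing requires rapport to come from the same visit as PTS. The first-phase rationale for sessions 2 and 4, and the description of the session-5 UCLA as the score following the first four sessions, point toward pairing early rapport with later PTS. On that reading three of the four models can be run.

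The wording is also permissive and the analysis secondary. An analyst would meet the empty pre-treatment cell at once, so that part is unlikely to mislead anyone. This is fair, and it limits the weight of the point. The choice of mediator occasion and informant remains open, and it could be made after the results are seen.

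On covariates, a reader might infer that the plan overlooks confounders altogether. It does not: the same section lists gender, age and number of trauma types. But it lists them for the trajectory models, and nothing carries them over to the mediation regressions.

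Lastly, the simulated rates rest on assumed correlations, and the high ones need the strongest of these. In the worst case, session-4 rapport does little better than concurrent rapport (28.5% against 32.5%). Early measurement reduces the scope for reverse causation but does not exclude it. These rates should not be used to judge how serious the point is.

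**Conclusion.** The point holds as a limited inconsistency plus an incomplete specification. One of the four stated mediation analyses cannot be run under any reading. Three of the four cannot be run if same-visit rapport is meant, but the plan does not state that rule and its own rationale leans away from it. The pairing of rapport with PTS, the TASC-R informant and the mediation covariates are left open. The UCLA informant is less so, since caregiver report is named as primary.

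The count comes from the documents alone. Everything said about false mediation rates depends on assumed values and serves only to show why timing and baseline adjustment can matter. The main group comparison on PTS is not touched. The correction should be made before analysis because it is cheap and removes a choice that could otherwise follow the data.

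**What to change.** In the mediation paragraph of section 5.2 (Statistical methods):

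1. Replace the reference to all four assessments with the three post-baseline PTS assessments: session 5, session 9 and post-treatment.
2. Name session-4 TASC-R as the mediator, with session 2 as a sensitivity analysis, in line with the first-phase rationale under Measures.
3. Name the TASC-R informant, and use caregiver-report UCLA as the outcome.
4. Adjust both the mediator and the outcome regression for baseline caregiver UCLA, gender and age. Consider number of trauma types, as already listed for the trajectory models.
5. Label any model that uses post-treatment rapport as concurrent and exploratory.
6. Keep the bootstrap or Monte Carlo interval.

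The cost is SAP wording only, since all these variables are already scheduled for collection. The plan should state the downsides:

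- Changes in rapport after session 4 are missed.
- Session-4 rapport can still reflect unmeasured symptom change up to that session and, for the child form, including it.
- The session-5 model is close to concurrent; session 9 and post-treatment are better separated.
- Baseline adjustment gains little if baseline UCLA is only weakly related to rapport and later PTS, which is possible because the entry threshold restricts its range.

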## **Statistical Plan**

#### **5.1 Number of Subjects**

60 participant youth

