#### **5.2 Sample size determination**

Although a primary objective of this study is to derive effect size estimates that can inform the design of a larger clinical trial, a preliminary power analysis was conducted. Results indicated that the proposed sample of 60 participants (equal sample sizes across the two conditions) can achieve 80% power to detect an approximately 5 point difference of pre-post change between the groups on the PTS measure (i.e., UCLA) when the standard deviation of each group is assumed to be 6.5 and the significance level is set at .05. Ethnic and gender composition will likely reflect those of the larger Harrisburg area (45% White, 45% African-American, 10% other ethnicities; 50% female, 50% male).

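### The rapport mediation analysis names no covariates, so a baseline factor such as PTS severity can bias the indirect effect if the dog changes rapport

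*Combined protocol and SAP*

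**What the plan says.** The last part of section 5.2 Statistical methods allows regression-based mediation at each of the four assessment sessions, to "examine if therapeutic rapport mediates the relationship between the presence of the dogs and PTS outcomes". It names a bootstrap or Monte Carlo test of the indirect effect and a SAS macro. It gives no covariates, informant pairing or sensitivity analysis. The ECG model just before it does have its covariates listed.

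Adjustment for confounders appears once, earlier in the same section, as part of the multilevel trajectory models. The examples there are gender, age and number of trauma types.

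Under Measures, item (10), rapport "will be assessed via child and caregiver-report using the appropriate versions of the Therapeutic Alliance Scale for Children-Revised". It is taken at sessions 2 and 4 and at post-treatment, and the item says that AAT is thought to help rapport develop. Under item (1), caregiver UCLA is the main PTS measure, and "Children will also complete the self-report version of the UCLA at each of the four assessment points". Section 4.2 Study Procedures assigns each child at random to one of two clinicians, who treat in both arms.

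**The concern.** A mediation analysis multiplies two paths: dog to rapport, and rapport to PTS with arm held fixed. Randomisation protects the first path and the overall arm comparison. It does not protect the second, because children are not allocated to levels of rapport. Anything that influences both rapport and later PTS enters that path.

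Three candidates are visible in the design:
- **Baseline PTS severity** may affect both how a child bonds and the later score.
- **Clinician:** rapport is with the clinician, and the two clinicians may also differ in outcome. Using the same two in both arms protects the arm comparison, not this path.
- **Informant:** child and caregiver each report both scales, so one person's reporting style can link them.

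Section 5.2 Sample size determination makes effect-size estimates for a larger trial a primary objective. A spurious mechanism, in either direction, could misdirect that trial's hypotheses and choice of measures.

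**Working it through.** **The plan's own figure.** The inputs are "60 participant youth" (30 per arm), an "approximately 5 point difference of pre-post change between the groups", and that "the standard deviation of each group is assumed to be 6.5" and "the significance level is set at .05" (taken as two-sided). The standard error is 6.5 × √(2/30) = 1.678. At 5 points, 5/1.678 = 2.98, and power is 84.6% (normal) or 83.4% (t). The difference detectable at 80% power is 4.70 (normal) or 4.78 (t) points, so the stated 80% reproduces as an approximation. It concerns the arm comparison; the mediation has no stated figure.

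**Model for the check.** All variables are standardised. X is arm (30/30), B baseline PTS, M rapport and Y later PTS:
- M = aX + r_BM·B + error
- Y = r_BY·B + error

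Neither dog nor rapport affects Y, so the true indirect effect is zero. The documents give no value for a, r_BM or r_BY. I assumed a = 0.5 or 0.8 SD, and (r_BM, r_BY) = (-0.2, 0.4), (-0.3, 0.5) and (-0.4, 0.6).

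**Bias in closed form.** Given arm, M has variance 1 and its covariance with Y is r_BM × r_BY. The unadjusted indirect effect is therefore centred on a × r_BM × r_BY, not zero. If the outcome is change (Y - B), it is centred on a × r_BM × (r_BY - 1), which has the opposite sign.

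| a | r_BM, r_BY | Bias, final score | Bias, change score | False mediation, unadjusted | With B in both equations |
|---|---|---|---|---|---|
| 0.5 | -0.2, 0.4 | -0.040 | +0.060 | 3.8% | 1.7% |
| 0.5 | -0.3, 0.5 | -0.075 | +0.075 | 8.8% | 1.8% |
| 0.5 | -0.4, 0.6 | -0.120 | +0.080 | 21.0% | 1.9% |
| 0.8 | -0.2, 0.4 | -0.064 | +0.096 | 7.0% | 3.3% |
| 0.8 | -0.3, 0.5 | -0.120 | +0.120 | 16.7% | 3.5% |
| 0.8 | -0.4, 0.6 | -0.192 | +0.128 | 40.1% | 3.6% |

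The last two columns are for final scores: 3,000 simulated trials per setting, with a 95% Monte Carlo interval for the product of paths. Repeat simulations of the same settings widen the ranges to about 4-22% (0.5 SD) and 7-42% (0.8 SD) unadjusted, against about 2-6% adjusted.

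**Reference points.**
- With no confounding the test is conservative: 2.3% at a = 0.5 and 4.2% at a = 0.8. The low-end rates should be read against these as well as against 5%.
- With a = 0 there is no systematic bias. The false rate stays below 2% at the correlations above, and at most 4.8% even with both correlations at 0.7 in size.
- If 6.5 is also used as the SD of final scores (an extra assumption), the largest bias is 0.192 × 6.5, about 1.2 UCLA points, or a quarter of the 5-point difference.

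**Clinician.** If the two clinicians differ by 0.8 SD on both rapport and PTS, the false rate is 6.5-13.0% unadjusted and 1.5-4.2% adjusted. At 0.3-0.5 SD there is little inflation. Same-informant bias was not quantified.

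**The case against.** **Silence is not a decision.** A reader might infer that the regressions will be run unadjusted. The plan says only that they can be conducted and names no covariates; it does not exclude any. The point is therefore that adjustment is unspecified.

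**Direction.** A reader might go on to infer that the trial would falsely credit the dog with working through rapport, because severe cases bond less and stay worse. The documents do not support this. Nothing in them says that severe cases bond less. The outcome is given only as PTS outcomes, while the sample size section speaks of pre-post change. With change scores the bias in this model is +0.06 to +0.13 SD, and false positives (about 5-24%) point to rapport being harmful. Bias remains under both readings, but its sign is not fixed.

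**Size.** Entry requires a caregiver UCLA score of at least 39, which narrows the range of baseline severity. If the assumed correlations describe an unrestricted population cut at its mean (a further assumption), the unadjusted rates fall to about 3-6% (0.5 SD) and 6-12% (0.8 SD). This stands as a caution: the highest figures belong to the strongest assumed correlations among the children actually enrolled.

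**Other causes.** Clinician is randomly assigned, so it is not tied to severity, and it matters only if the two clinicians differ clearly on both variables. Informant bias is plausible but has no figure.

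**Importance.** The analysis is optional and secondary. That limits the weight of the point but does not remove it, because the remedy uses data already collected.

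**Conclusion.** The concern holds in a conditional form. The plan names no covariates for the mediation, and the adjustment it describes elsewhere is tied to other models and lists neither baseline PTS nor clinician. If the dog changes rapport, and a baseline factor affects both rapport and later PTS, the indirect effect is biased even when rapport does nothing.

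For final scores under the assumptions shown, false mediation runs from little above the unconfounded rate to about 22% (dog effect 0.5 SD) or 42% (0.8 SD), and baseline adjustment brings it back to about 2-6%. These figures rest on assumed correlations and an assumed dog effect, and they cover baseline PTS only. Item (10) makes a dog effect on rapport plausible but gives no size. The main comparison of the arms is not touched. This should be fixed before analysis.

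**What to change.** Add to the mediation paragraph of section 5.2 Statistical methods:
- In both equations, include baseline UCLA from the same informant as the outcome, plus clinician, age and gender.
- Restrict the analysis to post-baseline PTS assessments. Rapport is not measured at pre-treatment, and baseline UCLA cannot be both outcome and covariate there.
- State whether the outcome is the final or the change score.
- Report the cross-informant pairing (child TASC-R with caregiver UCLA) alongside the same-informant pairing as a sensitivity check. Covariates alone do not remove shared reporting style.
- Label the result exploratory, because unmeasured rapport-PTS confounding remains. Adjustment also cannot establish time order where rapport and PTS are both taken at post-treatment.

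The cost is SAP wording and about four degrees of freedom (one each for baseline UCLA, clinician, age and gender) out of 60 youth. No new data are needed.
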